10.7.2.1. Handling of Missing and Partial Dates

Element	Reporting Detail
General	
 Partial dates will be displayed as captured in subject listing displays.
Adverse Events	
 Missing or Partial start/end date and time are not expected for Adverse events.
Concomitant Medications/ Medical History	
Partial dates for any concomitant medications recorded in the CRF will be imputed using the following convention:
 
 If the partial date is a start date, a '01' will be used for the day and 'Jan' will be used for the month If the partial date is a stop date, a '28/29/30/31' will be used for the day (dependent on the month and year) and 'Dec' will be used for the month. 
The recorded partial date will be displayed in listings.
 
 For assigning periods:

Element	Reporting Detail
	
• If start date is completely missing, then we assume the medication has been taken from the beginning of the study• If stop date is completely missing, then we assume the medication has been taken until the end of the study 
If start and stop date are completely missing, then we assume the medication has been taken for the duration of the study

10.8. Appendix 8: Values of Potential Clinical Importance

The values of potential clinical importance for Laboratory, ECG and Vital signs are listed in this section.

10.8.1. Laboratory Values

Haematology				
Laboratory Parameter	Units	Category	Clinical Concern Range	
			Low Flag (< x)	High Flag (>x)
Hematocrit	%	Male	<37	>50
		Female	<33	>45
		Δ from BL	N/A	> 7.5%
Hemoglobin	g/L	Male	<130	>170
		Female	<115	>155
		Δ from BL	N/A	> 30 g/L
Lymphocytes	x10 ⁹ /L		<1.2	>3.65
Neutrophils	x10 ⁹ /L		<2	>7.5
Monocytes	x10 ⁹ /L		<0.2	>1
Basophils	x10 ⁹ /L		<0.0	>0.1
Platelet Count	x10 ⁹ /L		<150	>400
White Blood Cell Count (WBC)	x10 ⁹ /L		<3.0	>10
Red Blood Cell Count (RBC)	x10 ¹² /L	Male	<4.4	>5.8
		Female	<3.95	>5.15

Clinical Chemistry				
Laboratory Parameter	Units	Category	Clinical Concern Range	
			Low Flag (< x)	High Flag (>x)
Albumin	g/L		< 34	> 50
Calcium	mmol/L		< 2.2	> 2.6
Creatinine	umol/L	Male	< 66	> 112
		Female	< 49	> 92
Glucose (Fasted)	mmol/L		< 3.9	> 5.8
Magnesium	mmol/L		< .6	> 1
Phosphate	mmol/L		< 0.87	> 1.45
Potassium	mmol/L		< 3.5	> 5.1
Sodium	mmol/L		< 135	> 145
Gamma GT	g/L		< 7.7	> 17.3

Liver Function				
Test Analyte	Units	Category	Clinical Concern Range	
			Low Flag (< x)	High Flag (>x)
Alkaline phosphatase	U/L	Female	< 35	> 104
		Male	< 40	> 129
AST/SGOT	U/L	Male	< 0	> 37
		Female	< 0	> 31
ALT/SGPT	U/L	Male	< 10	> 50
		Female	< 10	> 35
Total Bilirubin	µmol/L		< 0	> 20
Direct Bilirubin	µmol/L		< 0	> 20
Total Protein	g/L		< 63	> 83

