**DIAGNOSTIC ASSESSMENTS AND OTHER CRITERIA**

14. Subjects with renal function defined as Chronic Kidney Disease Epidemiology Collaboration (CKD-EPI) with an age appropriate GFR  $\leq 90$  (ml/min/1.73m^2).
15. Presence of Hepatitis B surface antigen (HBsAg) or Positive Hepatitis C antibody test result at screening.
16. Positive human immunodeficiency virus (HIV) antibody test.
17. Positive pre-study drug/alcohol screen.
18. Presence of clinically significant haematuria and/or proteinuria.

19. Carbon monoxide levels indicative of smoking or history or regular use of tobacco- or nicotine-containing products within 3 months prior to screening.
20. Abnormally low blood pressure as determined by the Principal Investigator
21. **Part A (Food Effect) Cohort 3 only:** Participant must have no dietary restrictions (e.g., lactose intolerance) or inability to eat an adapted standard meal (includes 35-40% fat content).
22. **Part A (Food Effect) Cohort 3 only:** History of gall bladder surgery or gall bladder removal, or history of an acute disease state (e.g. cholelithiasis) within 14 days prior to receiving the study treatment.
23. **Part B only:** Early morning cortisol < 420 nmol/L and inadequate response (rise of <250mmol/L from baseline) to ACTH stimulation test at Day -1.

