### **8.1.3. Renal Withdrawal Criteria**

A participant that meets any of the following bulleted criteria will be withdrawn from the study:

- New onset of any clinically significant and persistent haematuria / proteinuria (Spot Urine Protein Creatinine (UPC) ratio  $>0.5$ ) in the absence of another clinical explanation e.g. calculus / infection. If trace proteins are detected, repeat test should be performed within 24 hours.
- If there is any change in serum creatinine  $> 26 \mu\text{mol/L}$  (0.3 mg/dl) from baseline or  $> 50\%$  from baseline. If change in serum creatinine measures at  $> 26 \mu\text{mol/L}$  (0.3 mg/dl), repeat within 24 hours. If confirmed, the participant will be withdrawn, and further investigations will be performed.
- Persistent hypophosphataemia (less than 0.8mmol/L) confirmed by repeat testing. If a participant meets the withdrawal criteria for hypophosphataemia, then further investigations will be performed.

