**Table 7      Protocol-Required Safety Laboratory Assessments**

Laboratory Assessments	Parameters			
Hematology	Platelet Count	RBC Indices: Mean Corpuscular Volume (MCV) Mean Corpuscular Haemoglobin (MCH) %Reticulocytes	WBC count with Differential: Neutrophils Lymphocytes Monocytes Eosinophils Basophils	
	RBC Count			
	Hemoglobin			
	Hematocrit			
Clinical Chemistry 	BUN	Potassium	Aspartate Aminotransferase (AST)/ Serum Glutamic-Oxaloacetic Transaminase (SGOT)	Total and direct bilirubin
	Creatinine	Sodium	Alanine Aminotransferase (ALT)/ Serum Glutamic-Pyruvic Transaminase (SGPT), Gamma GT	Total Protein
	Glucose (Fasted) 	Calcium	Alkaline phosphatase	Albumin
	Magnesium	Phosphate	Creatine phosphokinase (CPK)	C-reactive protein (CRP)
	
 
• Specific gravity
 
• pH, glucose, protein, blood, ketones by dipstick
 
• Microscopic examination (if blood or protein is abnormal)
 
• Urine Protein : Creatinine ratio, if trace urine protein is identified by dipstick
 
• Urine creatinine
 
			
Routine Urinalysis				

Laboratory Assessments	Parameters
	
 
• Urine phosphate
 

Safety Biomarkers 	
 
• Kidney injury molecule 1 (KIM1)
 
• Neutrophil gelatinase-associated lipocalin (NGAL)
 
• Urine albumin
 

ACTH test 	
 
• Cortisol
 

Other Tests	
 
• Follicle-stimulating hormone and oestradiol (as needed in women of non-childbearing potential only)
 
• Alcohol breath test and urine drug screen (to include at minimum: amphetamines, barbiturates, cocaine, opiates, cannabinoids and benzodiazepines)
 
• Serology (HIV 1 & 2 antibody, hepatitis B surface antigen [HBsAg], and hepatitis C virus antibody).
 
• Estimated glomerular filtration rate (eGFR) will be calculated using the CKD-EPI formula
 
 
The results of each test must be entered into the CRF.

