3.1.1.2. Informal interim analysis

An informal interim analysis (IA) after completion of Part A will be conducted prior to initiation of Part B. This analysis will support the decision to progress, or, not progress to Part B and will consist of the following statistical displays on blinded safety and blinded PK data. Safety tables will therefore be presented by period rather than treatment to maintain the blind of the study.

Table 1: Planned Statistical Displays for the Interim analysis

Sl. No.	Population	IDS / Example Shell	Title	Responsible function
1	Safety	ES1A	Summary of Participant Disposition for the Participant Conclusion Record – Part A (Cohort 1 and Cohort 2 only)	Biostatistics
2	Safety	ES3	Listing of Reasons for Study Withdrawal – Part A (Cohort 1 and Cohort 2 only)	Biostatistics
3	Safety	SD3	Listing of Reasons for Study Treatment Discontinuation – Part A (Cohort 1 and Cohort 2 only)	Biostatistics
4	Safety	DM3	Summary of Demographic Characteristics – Part A (Cohort 1 and Cohort 2 only)	Biostatistics
5	Safety	DM4	Listing of Demographic Characteristics - Part A (Cohort 1 and Cohort 2 only)	Biostatistics
6	Safety	EX1	Summary of Exposure to Study Treatment - Part A (Cohort 1 and Cohort 2 only)	Biostatistics
7	Safety	EX4	Listing of Exposure Data – Part A (Cohort 1 and Cohort 2 only)	Biostatistics
8	Safety	AE1CP	Summary of All Adverse Events by System Organ Class and Preferred Term - Part A (Cohort 1 and Cohort 2 only)	Biostatistics
9	Safety	AE9	Listing of All Adverse Events - Part A (Cohort 1 and Cohort 2 only)	Biostatistics
10	Safety	EG4	Listing of All ECG Values for Subjects with Any Value of Potential Clinical Importance - Part A (Cohort 1 and Cohort 2 only)	Biostatistics
11	Safety	EG6	Listing of All ECG Findings for Subjects with an Abnormal Finding - Part A (Cohort 1 and Cohort 2 only)	Biostatistics
12	Safety	LB6	Listing of All Laboratory Data for Participants with Any Value of Potential Clinical	Biostatistics

			Importance – Part A (Cohort 1 and Cohort 2 only)	
13	Safety	UR2B	Listing of All Urinalysis Data for Subjects with Any Value of Potential Clinical Importance - Part A (Cohort 1 and Cohort 2 only)	Biostatistics
14	Safety	VS5	Listing of All Vital Signs for Subjects with values Potential Clinical Importance - Part A (Cohort 1 and Cohort 2 only)	Biostatistics
15	Safety	EG6 (to be modified for telemetry data)	Listing of Telemetry findings - Part A (Cohort 1 and Cohort 2 only)	Biostatistics

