5.2.1. Derivations and Handling of Missing Baseline Data

Definition	Reporting Details
Change from baseline in the study	
Change from Baseline	= Post-dose visit value – Baseline value
% Change from Baseline	= $100 \times [(Post-dose visit value – Baseline value) / Baseline value]$
Change from baseline within a period	
Change from Baseline in Period X	= Period X Post-dose value – Period X baseline value

% Change from Baseline in Period X	= $100 \times [(Period\ X\ Post-dose\ value - Period\ X\ baseline\ value) / Period\ X\ baseline\ value]$
------------------------------------	--

NOTES:

- Unless otherwise specified, the baseline definitions specified in Section 5.2 Baseline Definitions (the baseline of the study and the baseline of each period (unadjusted)) will be used for derivations for endpoints / parameters and indicated on summaries. Unless otherwise stated, if baseline data is missing or post-dose data is missing no derivation will be performed and (%) change from baseline will be set to missing.
- The relevant baseline definition will be footnoted on all displays involving change from baseline.

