10.8.2. ECG

ECG Parameter	Units	Clinical Concern Range	
		Lower	Upper
Absolute			
Absolute QTcF during the study (i.e. post dose)	msec		>500
Absolute PR Interval	msec	< 110	>220
Absolute QRS Interval	msec	< 75	>120
Change from Baseline			
Increase from Baseline QTc	msec		>60

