27.	Safety	COMP2	Listing of Compliance Based on Exposure –Part B		
Adverse Events					
28.	Safety	AE9	Listing of All Adverse Events – Part A	ICH E3	IA, SAC

ICH: Listings					
No.	Population	IDSL / Example Shell	Title	Programming Notes	Deliverable
29.	Safety	AE8	Listing of All Adverse Events – Part B	ICH E3	SAC
30.	Safety	AE7	Listing of Subject Numbers for Individual Adverse Events – Part A	ICH E3	SAC
31.	Safety	AE7	Listing of Subject Numbers for Individual Adverse Events – Part B	ICH E3	SAC
Serious and Other Significant Adverse Events					
32.	Safety	AE8CP	Listing of Serious Adverse Events – Part A	ICH E3	SAC
33.	Safety	AE8CP	Listing of Serious Adverse Events – Part B	ICH E3	SAC
34.	Safety	AE14	Listing of Reasons for Considering as a Serious Adverse Event- Part A	ICH E3	SAC
35.	Safety	AE14	Listing of Reasons for Considering as a Serious Adverse Event- Part B	ICH E3	SAC
36.	Safety	AECP8	Listing of Adverse Events Leading to Withdrawal from Study – Part A	ICH E3	SAC
37.	Safety	AECP8	Listing of Adverse Events Leading to Withdrawal from Study – Part B	ICH E3	SAC
38.	Safety	AECP8	Listing of Adverse Events Leading to Permanent Discontinuation of Study Treatment – Part A	ICH E3	SAC
39.	Safety	AECP8	Listing of Adverse Events Leading to Permanent Discontinuation of Study Treatment – Part B	ICH E3	SAC
Hepatobiliary (Liver)					
40.	Safety	MH2	Listing of Medical Conditions for Subjects with Liver Stopping Events - Part A	IDSL	SAC

ICH: Listings					
No.	Population	IDSL / Example Shell	Title	Programming Notes	Deliverable
41.	Safety	MH2	Listing of Medical Conditions for Subjects with Liver Stopping Events - Part B	IDSL	SAC
42.	Safety	SU2	Listing of Substance Use for Subjects with Liver Stopping Events - Part A	IDSL	SAC
43.	Safety	SU2	Listing of Substance Use for Subjects with Liver Stopping Events - Part B	IDSL	SAC
All Laboratory					
44.	Safety	LB6	Listing of All Laboratory Data for Participants with Any Value of Potential Clinical Importance – Part A	ICH E3 Display ALL chemistry data for a subject who experienced a value of potential clinical importance.	IA, SAC
45.	Safety	LB5	Listing of All Laboratory Data for Participants with Any Value of Potential Clinical Importance – Part B	ICH E3 Display ALL chemistry data for a subject who experienced a value of potential clinical importance.	SAC
46.	Safety	LB6	Listing of Laboratory Values of Potential Clinical Importance – Part A		SAC
47.	Safety	LB5	Listing of Laboratory Values of Potential Clinical Importance – Part B		SAC

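### Two SAP safety rules are wrong as written (the Gamma GT unit and the Part A worsening-AE window), and two laboratory flag rows need a stated direction or an added line

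*SAP*

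**What the plan says.** **Gamma GT.** SAP 10.8.1 sets flags below 7.7 and above 17.3 with the unit g/L. The same appendix gives alkaline phosphatase, AST and ALT in U/L. Protocol Table 7 puts the test in the same entry as ALT: "Serum Glutamic-Pyruvic Transaminase (SGPT), Gamma GT".

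**Worsening events in Part A.** SAP 10.4.2 says that an event starting in one period and worsening in a later one counts in both. Its logic for the later period then requires the worsening date to lie between that period's treatment start and the study treatment stop date. New-onset events have a start condition and no upper limit. SAP 10.4.1 runs the treatment phase to 24 hours after the dose. For the interim, it ends a period just before the next period's first dose.

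**Haemoglobin and haematocrit.** The haemoglobin change row reads "from BL N/A > 30 g/L", so the low flag is not applicable. The haematocrit row has the same form with 7.5%. SAP 5.2.1 defines change as "Post-dose visit value – Baseline value". The ECG table in SAP 10.8.2 does name a direction: "Increase from Baseline QTc".

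**Creatinine.** SAP 10.8.1 has absolute limits only: below 66 or above 112 µmol/L in men, below 49 or above 92 µmol/L in women. Protocol 8.1.3 works on change: "If there is any change in serum creatinine" exceeds 26 µmol/L or 50% of baseline, with a repeat test for the first.

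**Where the flags are used.** They drive the worst-case PCI tables (SAP 10.12.5), the "Listing of Laboratory Values of Potential Clinical Importance" (Listings 46–47), and row 12 of the interim displays, "Listing of All Laboratory Data for Participants with Any Value of Potential Clinical" Importance.

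**The concern.** Safety is the primary objective, and these rules filter or allocate its data.

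A Gamma GT limit in the wrong kind of unit gives either no flags or meaningless ones.

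The worsening rule matters because each participant in Cohorts 1 and 2 receives ascending doses and one placebo. An event that begins at one dose, or on placebo, and worsens the day after a higher dose would be summarised only under the earlier treatment. The by-dose table would then understate the higher dose, contrary to the SAP's own statement that such an event counts in both periods.

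For the laboratory rows, kidney effects and gastric erosion are listed risks in Protocol 3.3.1. A large haemoglobin fall or a creatinine rise is the kind of change a reader of these displays looks for. Row 12 is the only blood-laboratory display in the Part A interim, and the change-from-baseline tables come only at final analysis.

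**Working it through.** **Gamma GT.** No arithmetic applies. The unit g/L appears in SAP 10.8.1 for haemoglobin, albumin and total protein. Every other enzyme with a row there is in U/L. The documents show the mismatch but do not give the correct limits.

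**Worsening window.** Inputs: one dose on Day 1 of each period and at least 10 days between doses (Protocol Table 1); half-life about 1.3 h (SAP 10.4.1); dosing and event times used if collected (SAP 10.4.2).
- The plan's own figure reproduces: 5 × 1.3 h = 6.5 h, and max(6.5, 24) = 24 h.
- With a single dose, treatment start and stop coincide. The window is Day 1 by date, or stop − start = 0 h by clock time.
- Compare the 24 h treatment phase, the interval of at least 10 days to the next dose, and the 14–21 days to follow-up in the last period.
- Second reading: if the stop date means the last dose of the study, only worsening after the final-period dose is lost. As planned, that is 1 of the 3 later periods in Cohorts 1–2 and the only later period in Cohort 3. The text ties the logic to the later period's treatment dates, which favours the first reading.

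**Haemoglobin.** A 31 g/L fall gives a change of −31, which does not exceed +30. The haemoglobin rows miss it when baseline − 31 is at or above the absolute low limit.
- Men (130–170, 41 integer values): 130 + 31 = 161, so 161–170 are missed, 10 of 41.
- Women (115–155, 41 values): 115 + 31 = 146, so 146–155 are missed, 10 of 41.
- The absolute low flag catches the other 31 of 41 in each sex.
- Example: a man going from 168 to 132 g/L has a change of −36 and no haemoglobin flag.

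**Haematocrit.** The SAP does not say whether 7.5% is percentage points or relative.
- In points, falls beyond 7.5 can go unmarked from baselines above 37 + 7.5 = 44.5% (men) and 33 + 7.5 = 40.5% (women).
- If relative, from above 37/0.925 = 40.0% (men) and 33/0.925 = 35.7% (women).

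**Creatinine.** A 27 µmol/L rise is unmarked when baseline + 27 is at or below the high limit.
- Men (66–112, 47 values): 112 − 27 = 85, so 66–85, 20 of 47.
- Women (49–92, 44 values): 92 − 27 = 65, so 49–65, 17 of 44.
- The 50% limb adds nothing for in-range men, since 50% of 66 is 33, already above 26. It bites first only below a baseline of 52 (26/0.5), so for women at 49–51.
- Example: a man going from 80 to 110 µmol/L rises by 30 (37.5%) and stays under 112.

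The QTc change criterion of Protocol 8.1.6 (more than 60 msec) does have a matching flag row in SAP 10.8.2.

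**The case against.** The strongest reply is that the flags are not what protects participants.
- The investigator must review every laboratory report (Protocol 9.1.5).
- Individual laboratory safety tests are reviewed, with no PCI filter stated, at each Part A dose-escalation and safety-review meeting (Protocol 5.6.2; SAP 3.1.1.1 and 3.1.1.3).
- The dose escalation committee regularly reviews laboratory abnormalities (Protocol 8.1.8).
- The move to Part B rests on all available data (Protocol 5.6.3).
- Withdrawals are listed at the interim and at the end, renal biomarkers are listed for everyone (Listings 52–53), and Tables 3.9–3.10 and 3.13–3.14 summarise changes.
- The liver stopping criteria in Protocol Appendix 6 use ALT, bilirubin and INR, not Gamma GT.

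All of this stands. A reader might infer that the interim decision on Part B could be taken blind to a renal or haemoglobin signal, and the documents do not support that. The interim chemistry listing also prints all chemistry for anyone with any flagged value, so an unmarked creatinine may still be visible.

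On the individual items, the change symbol for haemoglobin names no direction, so a two-sided intention is possible. Rises-only follows from the sign convention, not from a stated choice. No text obliges PCI limits to repeat withdrawal criteria, so the creatinine row is an improvement and not an error. The worsening rule does not affect the interim, which has its own period definition. Measured against the 24 h treatment phase, the shortfall is about one day.

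A reader might also infer that excluding participants "with an age appropriate GFR" at or below 90 pushes creatinine baselines into the unmarked band. The documents give neither the CKD-EPI equation nor a creatinine distribution, so that inference is not made here.

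**Conclusion.** The point holds for safety displays and adverse-event attribution only. The Gamma GT row cannot be applied as written. The Part A worsening rule conflicts with the SAP's own treatment phase, its interim period end, its open-ended rule for new events and its stated intention to count in both periods. This rests on reading the stop date as the period's own; on the other reading the loss is confined to the last period. Either way, such events are probably few and remain in the adverse-event listing and in their first period's count.

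The haemoglobin and haematocrit rows are incomplete because direction and, for haematocrit, scale are unstated. The creatinine addition is optional and almost free. The counts of 10 of 41, 20 of 47 and 17 of 44 are integer baselines within the SAP limits; they are not proportions of participants, and the documents give no baseline distribution. No endpoint definition, estimate or stopping rule changes.

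**What to change.** - **SAP 10.8.1, Gamma GT:** replace the row with the testing laboratory's reference limits in U/L.
- **SAP 10.4.2:** set one explicit end for the later-period window, consistent with SAP 10.4.1. Just before the next period's dose, or follow-up for the last period, fits best with the open-ended rule for new events. If dose plus 24 hours is preferred, say so and apply it consistently.
- **SAP 10.8.1, haemoglobin and haematocrit:** state the direction of the change rows and whether 7.5% is points or relative. The sponsor should confirm what limit, if any, applies to falls, since the documents give none.
- **SAP 10.8.1, creatinine:** add a change-from-baseline display row that copies the thresholds already in Protocol 8.1.3, and state its direction. It marks values for display and creates no clinical rule.

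The cost is a few lines of SAP text and minor programming before final reporting. The data are already collected, and a few more values will be flagged and listed.

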#### **9.1.5.     Clinical Safety Laboratory Assessments**

Refer to [Appendix 2](#) for the list of clinical laboratory tests to be performed and to the SoA for the timing and frequency.

- The investigator must review the laboratory report, document this review, and record any clinically relevant changes occurring during the study in the AE section of the CRF. The laboratory reports must be filed with the source documents. Clinically significant abnormal laboratory findings are those which are not associated with the underlying disease, unless judged by the investigator to be more severe than expected for the participant's condition.
- All laboratory tests with values considered clinically significantly abnormal during participation in the study should be repeated until the values return to normal or baseline or are no longer considered significantly abnormal by the investigator or medical monitor.

- If such values do not return to normal/baseline within a period of time judged reasonable by the investigator, the etiology should be identified, and the sponsor notified.
- All protocol-required laboratory assessments (including tests for urine trace proteins and safety biomarkers), as defined in [Appendix 2](#), must be conducted in accordance with the SRM and the SoA.

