## 10.12. Appendix 6: Liver Safety: Required Actions and Follow-up Assessments

### Phase I liver chemistry stopping criteria and required follow up assessments

Liver Chemistry Stopping Criteria	
Required Actions and Follow up Assessments	
Actions	Follow Up Assessments

ALT-absolute
 
ALT<math>\geq</math>3xULN
 
If ALT<math>\geq</math>3xULN AND bilirubin <math>\geq</math> 2xULN (>35% direct bilirubin) or INR <math>>1.5</math>, Report as an SAE.
 
See additional Actions and Follow Up Assessments listed below
	
 
• Immediately discontinue study treatment
 
• Report the event to GSK within 24 hours
 
• Complete the liver event CRF, and complete an SAE data collection tool if the event also meets the criteria for an SAE
 
• Perform liver event follow up assessments
 
• Monitor the subject until liver chemistries resolve, stabilise, or return to within baseline (see MONITORING below)
 
 
MONITORING:
 
If ALT<math>\geq</math>3xULN AND bilirubin <math>\geq</math> 2xULN or INR <math>>1.5</math>:
 
 
• Repeat liver chemistries (include ALT, AST, alkaline phosphatase, bilirubin) and perform liver event follow up assessments within 24 hr
 
• Monitor subjects twice weekly until liver chemistries resolve, stabilise or return to within baseline
 
• A specialist or hepatology consultation is recommended
 
 
If ALT<math>\geq</math>3xULN AND bilirubin <math><</math> 2xULN and INR <math>\leq 1.5</math>:
 
 
• Repeat liver chemistries (include ALT, AST, alkaline phosphatase, bilirubin) and perform
 
 
 
• Viral hepatitis serology
 
• Obtain INR and recheck with each liver chemistry assessment until the transaminases values show downward trend
 
• Obtain blood sample for pharmacokinetic (PK) analysis, obtained within 12 hours of last dose
 
• Serum creatine phosphokinase (CPK) and lactate dehydrogenase (LDH).
 
• Fractionate bilirubin, if total bilirubin<math>\geq</math>2xULN
 
• Obtain complete blood count with differential to assess eosinophilia
 
• Record the appearance or worsening of clinical symptoms of liver injury, or hypersensitivity, on the AE report form
 
• Record use of concomitant medications on the concomitant medications report form including acetaminophen, herbal remedies, other over the counter medications.
 
• Record alcohol use on the liver event alcohol intake case report form
 
 
If ALT<math>\geq</math>3xULN AND bilirubin <math>\geq</math> 2xULN or INR <math>>1.5</math>:
 
 
• Anti-nuclear antibody, anti-smooth muscle
 

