10.12.5. Safety Tables

Safety: Tables					
No.	Population	IDSL / Example Shell	Title	Programming Notes	Deliverable
Adverse Events (AEs)					
3.1.	Safety	AE1CP	Summary of All Adverse Events by System Organ Class and Preferred Term – Part A	ICH E3	IA, SAC
3.2.	Safety	AE1	Summary of All Adverse Events by System Organ Class and Preferred Term – Part B	ICH E3	SAC
3.3.	Safety	AE3	Summary of Common (>=5%) Adverse Events by Overall Frequency – Part A	FDAAA, EudraCT	SAC
3.4.	Safety	AE3	Summary of Common (>=5%) Adverse Events by Overall Frequency – Part B	FDAAA, EudraCT	SAC
3.5.	Safety	AE1	Summary of All Drug Related Adverse Events by System Organ Class and Preferred Term – Part A	ICH E3	SAC
3.6.	Safety	AE1	Summary of All Drug Related Adverse Events by System Organ Class and Preferred Term – Part B	ICH E3	SAC
Serious and Other Significant Adverse Events					
3.7.	Safety	AE16	Summary of Serious Adverse Events by System Organ Class and Preferred Term (Number of Subjects and Occurrences) – Part A	FDAAA, EudraCT	SAC
3.8.	Safety	AE16	Summary of Serious Adverse Events by System Organ Class and Preferred Term (Number of Subjects and Occurrences) – Part B	FDAAA, EudraCT	SAC
Laboratory: Chemistry					
3.9.	Safety	LB1	Summary of Chemistry Changes from Baseline – Part A	ICH E3	SAC
3.10.	Safety	LB1	Summary of Chemistry Changes from Baseline – Part B	ICH E3	SAC

Safety: Tables					
No.	Population	IDSL / Example Shell	Title	Programming Notes	Deliverable
3.11.	Safety	LB17	Summary of Worst-Case Chemistry Results by PCI Criteria Post-Baseline Relative to Baseline – Part A	ICH E3	SAC
3.12.	Safety	LB17	Summary of Worst-Case Chemistry Results by PCI Criteria Post-Baseline Relative to Baseline – Part B	ICH E3	SAC
Laboratory: Haematology					
3.13.	Safety	LB1	Summary of Haematology Changes from Baseline – Part A	ICH E3	SAC
3.14.	Safety	LB1	Summary of Haematology Changes from Baseline – Part B	ICH E3	SAC
3.15.	Safety	LB17	Summary of Worst-Case Haematology by PCI Criteria Post-Baseline Relative to Baseline – Part A	ICH E3	SAC
3.16.	Safety	LB17	Summary of Worst-Case Haematology by PCI Criteria Post-Baseline Relative to Baseline – Part B	ICH E3	SAC
Laboratory: Urinalysis					
3.17.	Safety	LB1	Summary of Urine Concentration Changes from Baseline – Part A	ICH E3 Includes Baseline values.	SAC
3.18.	Safety	LB1	Summary of Urine Concentration Changes from Baseline – Part B	ICH E3 Includes Baseline values.	SAC
3.19.	Safety	UR3a	Summary of Urinalysis Dipstick and Microscopy Results – Part A		SAC

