3.20.	Safety	UR3a	Summary of Urinalysis Dipstick and Microscopy Results – Part B		SAC
3.21.	Safety	UR1	Summary of Worst-Case Urinalysis Results Post-Baseline Relative to Baseline – Part A	ICH E3	SAC
3.22.	Safety	UR1	Summary of Worst-Case Urinalysis Results Post-Baseline Relative to Baseline – Part B	ICH E3	SAC
Laboratory: Hepatobiliary (Liver)					

Safety: Tables					
No.	Population	IDSL / Example Shell	Title	Programming Notes	Deliverable
3.23.	Safety	LIVER1	Summary of Liver Monitoring/Stopping Event Reporting – Part A		SAC
3.24.	Safety	LIVER1	Summary of Liver Monitoring/Stopping Event Reporting – Part B		SAC
3.25.	Safety	LIVER10	Summary of Hepatobiliary Laboratory Abnormalities – Part A		SAC
3.26.	Safety	LIVER10	Summary of Hepatobiliary Laboratory Abnormalities – Part B		SAC
ECG					
3.27.	Safety	EG1	Summary of ECG Findings – Part A		SAC
3.28.	Safety	EG1	Summary of ECG Findings – Part B		SAC
3.29.	Safety	EG2	Summary of Change from Baseline in ECG Values by Visit – Part A	Includes Baseline values.	SAC
3.30.	Safety	EG2	Summary of Change from Baseline in ECG Values by Visit – Part B	Includes Baseline values.	SAC
Vital Signs					
3.31.	Safety	VS1	Summary of Change from Baseline in Vital Signs - Part A	ICH E3 Includes Baseline values.	SAC
3.32.	Safety	VS1	Summary of Change from Baseline in Vital Signs - Part B	ICH E3 Includes Baseline values.	SAC
3.33.	Safety	VS7	Summary of Worst-Case Vital Signs Results by PCI Criteria Post-Baseline Relative to Baseline – Part A		SAC
3.34.	Safety	VS7	Summary of Worst-Case Vital Signs Results by PCI Criteria Post-Baseline Relative to Baseline – Part B		SAC

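### The direct bilirubin high flag equals the total bilirubin flag (>20 µmol/L), so in a paired sample it adds nothing and a rise in direct bilirubin alone triggers no potential-clinical-importance (PCI) display

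*SAP*

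**What the plan says.** The Liver Function block of SAP 10.8.1 has one row for "Total Bilirubin" and one for "Direct Bilirubin". Both are in µmol/L, neither is split by sex, and both carry a low flag below 0 and a high flag above 20. For bilirubin the SAP sets no change-from-baseline criterion and no criterion on the direct share.

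Protocol Table 7 requires "Total and direct bilirubin" within clinical chemistry, so the two values are planned together.

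Displays that depend on the PCI flag:
- Tables 3.11 and 3.12, worst-case chemistry by PCI criteria.
- Listings 44 and 45. Listing 44 is the "Listing of All Laboratory Data for Participants with Any Value of Potential Clinical Importance – Part A", and Listing 45 is its Part B counterpart. A participant enters with at least one PCI value, and all of that participant's chemistry data are then shown.
- Listings 46 and 47, which show the PCI values themselves.

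Listing 44 is also an interim deliverable. In SAP 3.1.1.2, Table 1, this listing (shell LB6) is the only display of blood laboratory results planned for the informal interim before Part B, and it covers Cohorts 1 and 2.

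Displays that do not depend on the flag, judging by their titles, include the "Summary of Chemistry Changes from Baseline – Part A" (Table 3.9, with 3.10 for Part B) and the "Summary of Hepatobiliary Laboratory Abnormalities – Part A" (Table 3.25, with 3.26 for Part B). These are planned for the final analysis only.

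**The concern.** A flag on a component earns its place if it can fire when the flag on the whole does not. With identical limits it cannot. The direct bilirubin row looks like a separate check, but it works as a repeat of the total bilirubin row, restricted to the more extreme cases.

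What is at stake is which participants and values appear in the PCI tables and listings. Those displays are part of the safety reporting, and safety is the primary objective. A reader of Tables 3.11/3.12 who sees no flagged direct bilirubin could take that as evidence that direct bilirubin stayed unremarkable. The table can show only that it did not exceed the limit set for total bilirubin.

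**Working it through.** **Inputs.** Total high flag: T > 20 µmol/L. Direct high flag: D > 20 µmol/L. Both are strict inequalities (SAP 10.8.1). Both analytes come from the same chemistry panel (Protocol Table 7). By definition 0 ≤ D ≤ T.

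**Step 1, logic.** If D > 20 and T ≥ D, then T > 20. The set of samples flagged on direct bilirubin lies inside the set flagged on total. The low flag (below 0) cannot fire for a concentration.

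**Step 2, enumeration.** Take all pairs with 0 ≤ D ≤ T ≤ 100 in steps of 0.1. The number of pairs is 1001 × 1002 / 2 = 501,501.

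| Result | Count | Arithmetic |
|---|---|---|
| Both flags | 320,400 | 800 × 801 / 2 |
| Total only | 160,800 | 800 × 201 |
| Neither | 20,301 | 201 × 202 / 2 |
| Direct only | 0 | |

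The counts add to 501,501. They describe the rule, not how often such values occur in people.

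**Step 3, what passes unflagged.** With T ≤ 20, no direct share raises a bilirubin flag, even 100%. For illustration, T = 19 and D = 12 gives 12/19 = 63% direct, and neither row fires. Above 20 the total row fires first. At T = 40 the direct row joins it only if D exceeds 20, that is, more than 20/40 = 50% of total.

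**Step 4, consequence by display.** For a sample with raised D and T ≤ 20:
- Tables 3.11/3.12 and Listings 46/47: the value does not appear as a direct bilirubin abnormality.
- Listings 44/45, including the interim version of 44: the value does not by itself bring the participant in. If another analyte is flagged, the participant is listed and the direct value is shown with the rest of the chemistry.
- Tables 3.9/3.10: the value contributes to the group summary.
- Tables 3.25/3.26: the documents do not give the criteria behind these, so they cannot be counted either way.

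**The case against.** The case against giving this weight is that little depends on the flag, and most of that case stands.

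**A reader might infer that an isolated rise in direct bilirubin goes unseen.** The documents do not support that. Protocol 9.1.5 says "The investigator must review the laboratory report, document this review", and clinically relevant changes are recorded as adverse events. Laboratory safety tests are among the individual data considered at dose escalation meetings. Tables 3.9/3.10 do not use the flag. Alkaline phosphatase, ALT and AST have their own limits in SAP 10.8.1, and one flag on any of them brings the whole chemistry record into Listings 44/45. What remains true is narrower: Tables 3.9/3.10 are group summaries, and the individual laboratory listings are built on the PCI flag or, for Listings 48/49, confined to character results.

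**A reader might call the T = 19, D = 12 example a cholestatic pattern that the plan misses.** Nothing in the documents supports that label for an unflagged total with no other abnormality. If other liver tests were abnormal, their flags would bring the participant into Listings 44/45.

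**A reader might infer that the SAP contradicts the protocol's 35% rule.** It does not. The protocol reads the direct share only when total bilirubin is already raised: above 1.5 × ULN in exclusion criterion 4, and at 2 × ULN or more with ALT at 3 × ULN or more in Appendix 6, where the condition is ">35% direct bilirubin". Neither rule speaks to a total of 20 or below, unless the laboratory's ULN is much lower than 20. The documents do not state the ULN.

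**A reader might turn the 35% into an absolute limit, 0.35 × 20 = 7 µmol/L.** That figure has no source in the documents and does not reproduce the fraction. At T = 40, D = 8 is 20% direct and would be flagged. At T = 10, D = 6 is 60% direct and would not be.

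Finally, the redundancy needs a valid paired total. If total is missing, or assay error gives direct above total, the direct flag can fire alone.

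**Conclusion.** The defect holds in a limited form. In any sample with a valid total, the direct bilirubin flag contributes zero additional flagged results. A rise in direct bilirubin with total at or below 20 µmol/L is not recorded as a PCI value, and on its own it does not put the participant into any PCI-based listing, the interim one included.

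This rests on two assumptions. One is that total and direct are reported from the same sample, as Protocol Table 7 implies. The other is that the chemistry PCI displays cover the Liver Function block of SAP 10.8.1, which follows from the protocol classing both bilirubins as clinical chemistry.

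How many participants would be affected cannot be estimated, because the documents give no reference range for direct bilirubin. No stopping, liver-event or serious-event rule uses this flag, so participant protection does not rest on it. It is a reporting point of low severity, worth correcting because the correction is so small.

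**What to change.** In SAP 10.8.1, replace the direct bilirubin upper limit with the testing laboratory's own upper reference limit for direct bilirubin. Leave the total bilirubin row as it is. Settle the value before unblinding, so that the choice is not informed by treatment assignment.

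The cost is one table cell and a query to the laboratory. The PCI tables and listings then pick up the new limit without a change of design. The downside is that a few more values may be flagged, some of them clinically trivial. No extra sample is needed, and no stopping or management rule changes.
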